12.9 Medications

All cardiovascular medications must be documented at baseline, and any changes in medications must be documented at each scheduled follow-up visit. Cardiovascular medications include anticoagulants, antiplatelet agents, ACE inhibitors, angiotensin II receptor blockers or inhibitors, beta blockers, calcium channel blockers, diuretics, digitalis preparations, and any medication that may increase the risk of bleeding.

12.10 Clinical Laboratory Tests

Blood laboratory analyses must be done at baseline and each scheduled follow-up visit. Assessments include: NT-proBNP, plasma free hemoglobin, serum creatinine, and International Normalized Ratio (INR). Creatinine kinase-MB (CK-MB) and/or Troponin (Type I or T) should also be collected according to standard of care at the clinical site. Additionally, serum creatinine, INR, CK-MB/Troponin must be assessed at pre-discharge.

12.11 Electrocardiogram

A 12-lead ECG must be recorded at baseline, intraoperatively both before and after implant and at pre-discharge.

12.12 Adverse Events

All adverse events (AEs) that occur to any subject during study participation must be documented on an AE case report form (CRF). Refer to Section 0 below for further reporting requirements.

12.13 Vigilance Officer

[Redacted]

[Redacted]

[Redacted]

13 Implant Procedure

13.1 Requirements

The implant should be performed by the procedural heart team (See Section 10.1). The cardiac surgeon should be the primary operator.

The following equipment is required for implantation:

- Standard cardiac catheterization lab equipment
- Fluoroscopy equipment appropriate for use in cardiac interventions
- Transesophageal echocardiographic equipment
- Angiographic equipment

For backup purposes, the following are needed:

- Circulatory support
- Temporary pacing equipment
- Defibrillator

13.2 Preparation

The Tendyne Mitral Valve implant procedure is to be performed without cardiopulmonary bypass, however, it must be available for backup support if needed.

Prepare the subject for the implant procedure as follows:

- Administer general anesthesia.
- Attach a 12-lead ECG (if not obtained immediately prior).
- Prepare the subject for a left mini-thoracotomy.
- Prepare the subject for TEE.
- Prepare the subject for right- and left-heart catheterization.

The subject must be on anticoagulant typical for transcatheter therapeutic interventions. Activated clotting time (ACT) is to be maintained at >250 seconds for the duration of the procedure.

13.3 Initial Data Acquisition

Tendyne will provide specific instruction on intraoperative imaging and data acquisition requirements as part of investigator training. A brief overview is provided here.

Using cardiac catheters, obtain the required measurements, including the following:

- Cardiac output using thermodilution method

- Intracardiac and vascular pressures

Perform the intraoperative TEE protocol to obtain views and measurements pertaining to the mitral valve and left ventricular function.

13.4 Implant Procedure

An overview of the recommended Tendyne Mitral Valve implant procedure is provided here. Refer to the Instructions for Use for additional detail.

13.4.1 Valve Placement

1. Ensure that all components are fully de-aired to avoid introducing air emboli into the heart, and continue to flush them with isotonic saline throughout the procedure.
2. Thoroughly rinse the valve with heparinized isotonic saline.
3. Compress and load the valve into the instrument, ensuring that the proud anterior segment is properly aligned with the corresponding marker on the instrument.
4. Determine the proper trajectory from the patient's left ventricular apex to the mitral valve. Puncture the apex and insert a standard .035" guidewire.
5. Ensure a path clear of entanglement in the chordae.
6. Advance the instrument over the guidewire to achieve access to the left ventricle. Further advance it across the mitral valve and into the left atrium.
7. Deploy the valve, while observing the deployment using echo and/or fluoroscopic imaging.
8. Pull the valve proximally into the mitral annulus ensuring that the proud anterior cuff is oriented toward the aortic-mitral continuity.
9. Using echo and/or fluoroscopic imaging, confirm that the valve is oriented correctly.
 - a) If the valve needs to be repositioned, use the instrument to partially recapture the valve, push it up into the left atrium, reorient, and pull it back into position.
 - b) If the valve is the wrong size or otherwise needs to be withdrawn, use the instrument to fully recapture the valve and pull it out through the apical access. If desired, an alternative valve can be deployed.
10. Once proper orientation has been confirmed, adjust tension using the apical pad tool to attain proper seating of the valve for mechanical stability and optimal paravalvular sealing.
11. Once stability is achieved and valve function is determined to be acceptable, remove the instrument and fasten the apical pad to the tether.

13.4.2 Valve Verification

1. Monitor the function of the implanted valve with periodic TEE.
2. Measure the cardiac output and cardiac index.
3. Measure transmitral pressure gradient (mean and peak).
4. Measure aortic and right arterial (RA) pressures.
5. Optionally perform a left ventriculogram.

6. Perform an ECG.
7. Trim the tether proximal to the apical pad.
8. Close the surgical incision in the usual manner.

13.5 Post-Operative Care

In the immediate post-operative period, the subject's blood pressure is to be closely monitored and maintained below 135 mmHg systolic if possible.

Subjects are required to be on anticoagulation therapy, warfarin with a target INR range of 2.5 to 3.5, for a minimum of three months. Antiplatelet therapy may also be administered during this timeframe. Thereafter, subjects should be on aspirin alone or in combination with anticoagulation therapy.

14 Follow-up Visits

14.1 Pre-Discharge

Pre-discharge data collection is to be done within 24 hours prior to discharge (or, in the event of prolonged hospitalization, within 10 days after the implant procedure). Pre-discharge requirements include clinical status, medications, an ECG, and documentation of any peri-operative AEs. It is recommended that serum creatinine be assessed at approximately 48 hours post implant.

An Implant card will be delivered to the patient when required by National regulation per specific Tendyne instructions for implant card distribution and completion, as applicable.

14.2 Scheduled Follow-up Visits

Follow-up data must be documented using the appropriate eCRFs and image data must be submitted in electronic format.

Follow-up visits must occur at the following time points following implantation:

- Pre-discharge Within 24 hours prior to discharge or up to 10 days post-procedure, whichever occurs first
- One month 28 - 40 days
- Three months 90 ± 14 days
- Six months 180 ± 30 days
- One year 365 ± 45 days
- Two years 730 ± 60 days
- Annually thereafter until 5 years.

Subjects who have any part of the Tendyne Mitral Valve System introduced into the body but who do not end up with an implanted Tendyne Mitral Valve only need to be followed through one month or until resolution of any procedure or device related adverse event and then exited from the study. Subjects who are not exposed to the Tendyne Mitral Valve System will be exited from the study immediately. Documentation for subjects exited from the study must be completed using the appropriate CRF.

14.3 Study Exit

After the 2-year study visit, subjects should be followed annually until study completion and closure. Consistent with ongoing, interim communication with each patient's community care physician/cardiologist, upon study completion, each patient will be returned to the full care of such patient-identified physicians. The clinical study team shall remain available to each patient's community care physician in the event of any specific follow-up evaluations and consultations.

14.4 Unscheduled Follow-Up Visits

If a subject presents for an unscheduled visit due to an AE that is serious (SAE) and/or device- or procedure-related, the following are required: clinical status; medication changes; and documentation of the AE using the appropriate eCRFs.

14.5 Lost to Follow-Up

If a subject fails to comply with follow-up schedule, the site must make repeated attempts (at least three) to contact the patient. If a patient cannot be contacted anymore, the investigator should contact a third person (normally the patient's general practitioner) to get information about the patients' health. The permission and the contact details are stated in the Informed Consent form of the subject. Each attempt and the method used (e.g., telephone) must be documented in the patient's records. A subject who is lost to further follow-up must be reported to the sponsor using the appropriate eCRF.

14.6 Withdrawals

A subject may voluntarily withdraw from the study at any time. A subject may also be withdrawn from the study at the discretion of the investigator. In the event of withdrawal from the study, the investigator must ensure that the reason for the withdrawal is documented. If the subject had an AE, the subject must be followed until it is resolved, if possible, or until the investigator determines that the condition is stable. Withdrawn subjects will not be replaced.

All withdrawals must be reported to the sponsor using the appropriate eCRF.

15 Reinterventions and Explants

In the event that a subsequent procedure related to the Tendyne Mitral Valve is required at any time during a subject's study participation, the physician should obtain image data and otherwise attempt to characterize the valve *in situ*, to the extent feasible.

If an open-chest procedure is performed, then photographs should be taken. Photographs should be taken of the valve and/or native tissues before and after any modification or explant is done. The sponsor is particularly interested in understanding host response to the implanted valve (tissue ingrowth) and other device-host interfaces such as potential damage to native tissues including native leaflets, subvalvular structures and myocardium.

If a valve is explanted, the valve should immediately be placed in 10% neutral buffered formalin and returned to the sponsor for analysis. The valve must be handled carefully and as little as possible to prevent damage and preserve its integrity. The sponsor must be contacted for shipping and packaging materials and to arrange for transport.

All relevant data pertaining to the reintervention or explant must be documented on the appropriate eCRF. The physician should dictate an operative report and submit it to the sponsor along with any image data and photographs.

16 Heart Transplants or Subject Death

In the event of subject death or heart transplant, histological and engineering analyses of the *in situ* valve would provide valuable information. Therefore, a supplemental consent form may be used to authorize explant and donation of the heart to the sponsor. The sponsor must be contacted for shipping and packaging materials and to arrange for transport.

17 Data Management

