2.1 Executive Summary

The purpose of this expanded clinical study is to evaluate the performance and safety of the Tendyne Mitral Valve System in the treatment of severe mitral regurgitation in patients with functional disability greater than or equal to NYHA Class II, who are not suitable candidates for surgical replacement with otherwise available devices. The data gathered in this study will be used to support conformity requirements for CE Mark of the Tendyne Mitral Valve System, using an appropriately powered sample size to enable assessment of the study safety and performance endpoints of the Tendyne Mitral Valve System in the intended populations.

This study will be continued after the CE Mark to collect long-term safety and performance data as part of the Tendyne Mitral Valve System post-market follow-up program. All patients shall continue to be followed through 5 years in the post-market setting.

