8.4 Handling Study Discontinuations

Study drop-outs will be listed along with the reason for termination per Section 8.1 of the protocol. Drop-outs will be censored from the analysis with no data imputation. Deviations from the protocol will also be summarized by deviation type as well as total. The primary statistical analysis will be based on subject counts. A subject with more than one deviation will be counted only once toward the rate based on the total number of subjects with protocol deviations.

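### After an investigator withdraws an implanted subject, Protocol 14.6 does not require new deaths, reinterventions, strokes or heart-failure admissions to be collected

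*Protocol*

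**What the plan says.** Protocol 14.6 covers voluntary withdrawal and adds: "A subject may also be withdrawn from the study at the discretion of the investigator". It lists no permitted grounds. Three things must follow: "the investigator must ensure that the reason for the withdrawal is documented", the withdrawal is reported to the sponsor on an eCRF, and "If the subject had an AE, the subject must be followed until it is resolved, if possible" or the investigator judges the condition stable. "Withdrawn subjects will not be replaced".

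Protocol 14.5 deals with subjects who stop attending. The site makes at least three contact attempts. If these fail, "the investigator should contact a third person", normally the general practitioner, for information on the patient's health. "The permission and the contact details are stated in the Informed Consent form of the subject".

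Protocol 8.4 states the analysis consequence: "Drop-outs will be censored from the analysis with no data imputation". SAP 2.5 uses available data and generally does not impute endpoints in descriptive summaries.

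**The concern.** Stopping study visits does not end exposure, because the valve stays in. An investigator's decision to withdraw a subject is also not a withdrawal of consent. Yet a subject withdrawn this way is observed less than one who simply stops attending.

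The study is single-arm, so investigators know the treatment (the documents do not discuss blinding), and there is no control group in which similar losses might offset the bias. If withdrawal is related to prognosis, the subjects who drop out of view are not a random subset. The Clinical Events Committee and the core laboratories are independent, but they cannot assess events that nobody reports. No later analysis can recover status that was never collected.

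Protocol 7.3.3 gives the purpose of follow-up to 5 years as capturing rarer, unanticipated and time-related events. New events after withdrawal are of this kind.

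**Working it through.** The visible documents give no withdrawal rate or missing-data allowance, so there is no figure of the plan to reproduce. The check is a comparison of sections, followed by an illustration.

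**1. Lost versus withdrawn**

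| | Lost (14.5) | Withdrawn by investigator (14.6) |
|---|---|---|
| Contact attempts | At least three | None required |
| Third-party health check | Yes (worded as should) | None |
| Existing AE | Not addressed separately | Followed to resolution or stability |
| New death, reintervention, explant, stroke, heart-failure admission | May come to light through the third person | Not required |
| Administrative record | eCRF | Reason and eCRF |

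**2. Does another visible section close the gap?** No. Section 18 makes AEs reportable from enrolment to study exit. Section 15 asks for reintervention and explant data during study participation. Section 11.4 sets the follow-up of implanted subjects but has no rule for withdrawn ones.

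**3. What passive contact could supply, by endpoint**

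| Endpoint | Further data needed | What passive contact can do |
|---|---|---|
| Mortality at 30 days and 3 months | None | Settle it |
| Device success | Central MR, gradient or orifice area, LVOT gradient, paravalvular leak | Identify some failures; cannot establish success |
| Individual Patient Success, 1 year | Device success, NYHA, six-minute walk, KCCQ | Identify some failures; cannot establish success |
| 2-year safety composite | Device success | Identify some failures; cannot establish success |
| Long-term safety to 5 years | Detail of each event | Detect major events |

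**4. Illustrative bounds on mortality.** N = 86 is the minimum CE Mark report cohort in SAP 1.3. The known deaths d and the withdrawals w are assumptions. All w are taken to leave, with status unknown, before the time point considered.

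Reported rate (complete cases) = d/(N − w); lowest possible = d/N; highest possible = (d + w)/N.

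| w | d | Reported | Lowest | Highest |
|---|---|---|---|---|
| 4 | 12 | 12/82 = 14.6% | 12/86 = 14.0% | 16/86 = 18.6% |
| 9 | 12 | 12/77 = 15.6% | 12/86 = 14.0% | 21/86 = 24.4% |
| 13 | 18 | 18/73 = 24.7% | 18/86 = 20.9% | 31/86 = 36.0% |

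The width of the range is w/N whatever d is: 4/86 = 4.7, 9/86 = 10.5 and 13/86 = 15.1 percentage points. The number of withdrawals therefore drives the uncertainty, and it can only accumulate with time.

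**5. The 30-day mortality test.** SAP 2.2.3.1 gives a 20% goal. The significance level and analysis text are not visible, so I assume an exact (Clopper-Pearson) one-sided upper bound, the 1 − α quantile of Beta(x + 1, n − x), with n = 86.

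- α = 2.5%: 9/86 gives 18.9% (goal met); 10/86 gives 20.4% (not met). With 4 subjects left out, 9/82 gives 19.8% (met). One unseen death among the 4 makes it 10/86, 20.4% (not met).
- α = 5%: 10/82 gives 19.8% (met); one unseen death makes it 11/86, 20.3% (not met).

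This reversal occurs only at the boundary count and needs withdrawals and a death within 30 days. It is not general: with 9 left out, the largest passing count at α = 2.5% is 8/77, and one unseen death gives 9/86, which still passes.

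**The case against.** The other side has several good points.

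- **A reader might infer that every affected endpoint could be rescued by a telephone call.** The documents do not support that. Device success needs echocardiography, and Individual Patient Success also needs NYHA class, walk distance and KCCQ. Only mortality is fully recoverable.
- **A reader might infer that 14.6 contradicts the executive summary**, which says "All patients shall continue to be followed through 5 years in the post-market setting". That is a statement of intended follow-up, and a withdrawal clause does not contradict it. Section 11.4 already exits non-implanted subjects early, so the phrase is not literal in any case.
- **A reader might infer that an explant or a decline leading to withdrawal goes unrecorded.** An explant before withdrawal already fails device success and must be documented under section 15. A decline would normally be an AE, and 14.6 has it followed. A death that is the outcome of such an AE would be captured. The gap is new events, in subjects with no AE or after an earlier AE has resolved or stabilised.
- **A reader might infer that the consent permission already covers withdrawn subjects.** Section 14.5 describes it only for patients who cannot be contacted, and the consent pages were not available for review. Its wider scope is unknown.
- **Recording of withdrawals is largely in place.** Reasons are documented under 14.6 and tabulated under SAP 2.1.3, so no new data item is needed for that.
- **The counts are assumed.** Also, 8.4 says censored, which need not mean the complete-case denominators used above. That affects the reported rate but not the lowest and highest possible rates.

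Parts of the SAP and the protocol's section 23.10 on missing data are blacked out. A sensitivity analysis there could show the uncertainty but could not supply missing status. None of this changes what 14.6 requires after withdrawal.

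**Conclusion.** The point holds as a limited gap in data collection. Followed as written, 14.6 allows a subject carrying a permanent valve to leave without stated grounds, and does not require new major events to be sought afterwards. These events are not required to be collected; the text does not show that they will always be missed.

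The primary safety and performance endpoints are at 30 days, where exposure is small. It grows for 3-month mortality (a descriptive additional endpoint), the 1-year and 2-year composites, and safety to 5 years. The actual size cannot be stated. For scale, 4 to 9 unknown statuses among 86 subjects would leave a mortality range 4.7 to 10.5 percentage points wide. This does not threaten the trial's validity; it is an inexpensive improvement that should be made, because status is hard to reconstruct later.

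**What to change.** Amend Protocol 14.6:

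1. For subjects in whom the device was introduced, investigator-initiated withdrawal stops study visits and tests. Passive data collection continues for the rest of that subject's planned follow-up period.
2. Unless the subject revokes permission, use the 14.5 third-party route, or medical records, to collect vital status, mitral reintervention or explant, stroke, and heart-failure hospitalization.
3. Include subjects who withdraw voluntarily only as far as their consent allows.

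The cost is a short amendment, possible changes to consent wording so that the permission covers withdrawn subjects, and brief contacts for what should be a few subjects. Sample size, power and endpoint definitions stay as they are. For mortality, the ranges shown above would shrink towards the observed rate as unknown statuses are resolved. For the composites, some failures would be identified, but success would remain unconfirmed without the visits.

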17.1 Subject Identification

Each subject will be assigned a unique identification code (ID) for the purpose of identity protection. Any subject names that may inadvertently appear on study documents submitted to the sponsor will be redacted upon receipt.

17.2 Central Database

All study documentation will be collected and compiled in a central database. Appropriate quality control measures will be established to ensure accurate and complete transfer of information from the study documentation to the central database.

17.3 Electronic Case Report Forms (eCRF)

Electronic case report forms are designed to capture study data. The investigator is responsible for completing all appropriate sections of the eCRFs and submitting them to the sponsor in a timely manner. The investigator is also responsible for responding to queries (e.g., data clarification forms) from the sponsor to clarify any pending questions about the data.

17.4 Protocol Deviations

The investigator must document any deviation to this protocol using the appropriate eCRF. Study monitoring will include review for protocol deviations. Under emergency circumstances, deviations from the Study Protocol to protect the rights, safety and well-being of human subjects may proceed without prior approval of the sponsor and the EC. Such deviations shall be documented and reported to the sponsor and the EC as soon as possible.

An investigator must notify the sponsor and the reviewing institutional review board/ethics committee as soon as possible of any deviation from this protocol that was done to protect the life or physical well-being of a subject.

17.5 Centre Noncompliance

Protocol deviations will be closely monitored. If unacceptable deviations, repeated deviations, or other compliance problems are noted, the sponsor reserves the right to suspend study enrollment at that site until a sufficient system is in place to reduce further deviations and ensure compliance.

17.6 Data Processing and Management

Data will be reviewed manually and electronically for accuracy and completeness. Standard checks such as range checks will be incorporated into the central database. Data clarification Forms (DCF) will be issued to resolve data discrepancies. Study monitoring will be conducted to ensure that the site is submitting complete and accurate data, and to verify source data.

